8.1 Screening

Molecular pre-screening

Not applicable.

Screening

Written informed consent must be obtained before any study specific medical procedures are performed.

All screening/baseline assessments (with the exception of cytogenetic assessment of Bone Marrow Aspirate) should occur within 28 days before Week 1 Day 1.

The screening visit window for cytogenetic assessment Bone Marrow Aspirate (BMA) is 56 days prior to Week 1 Day 1. Should bone marrow assessments have been performed before the main informed consent is signed but within 56 days of Week 1 Day 1, no further bone marrow sampling will be required at screening and results from prior bone marrow assessment will be collected. At Week 48, and at end of treatment for patient completing trial for lack of efficacy, a bone marrow aspirate must be collected even if the screening/baseline bone marrow aspirate sample was not collected.

During the screening visit, inclusion and exclusion criteria will be assessed. Screening assessments to confirm eligibility must be performed prior to study enrollment. The results of the central real time quantitative polymerase chain reaction (RQ-PCR) and the local cytogenetic assessment (BMA, performed locally within 56 days of Week 1 Day 1) must be available prior to enrollment and first dose of study treatment. Central mutation analysis will be performed during the course of the study and data not available prior to enrollment.

Screening assessments include: demographics, laboratory baseline assessments (including hematology, chemistry, coagulation, serum pregnancy test and hepatitis markers), physical examination including extramedullary involvement, peripheral blood collection for BCR-ABL1 RQ-PCR, bone marrow aspirate for cytogenetic assessment (if prior bone marrow aspirate evaluation was more than 56 days before Week 1 Day 1) and CCI [REDACTED]. Other assessments includes performance status, ECG, echocardiogram, height, weight and vital signs, as well as evaluation of all relevant medical history including cardiovascular risk factors, CML disease history including T3151 mutation status, prior TKI therapy and antineoplastic medication. Assessment of prior and concomitant medication must be performed prior to the first dose of study treatment. For details of assessments required during screening please refer to [Table 8-1](#).

Patients with potassium, and/or magnesium and/or total calcium levels that are < LLN at screening, must have their potassium, and/or magnesium, and/or calcium replenished through supplementation and the levels must be within normal limits prior to the first dose of study drug.

A patient who has laboratory test (peripheral blood test) results that do not satisfy the entrance criteria may have the tests repeated. These tests may be repeated as soon as the investigator believes the re-test results are likely to be within the acceptable range to satisfy the entrance criteria, but should be completed within the screening window. In this case, the subject will not

be required to sign another Informed Consent Form (ICF), and the original patient ID number assigned by the investigator will be used. In the event that the laboratory tests cannot be performed within the screening visit window, or the re-tests do not meet the entrance criteria, or other eligibility criteria have changed and are not met anymore, the patient is considered a screen failure, and must be discontinued from the study.

A new ICF will need to be signed if the investigator chooses to re-screen the patient after a patient has screen failed and a new patient ID will be assigned. All required screening activities must be performed when the patient is re-screened for participation in the study. No further bone marrow sampling will be done at re-screening if a previous assessment was done within 56 days of Week 1 Day 1. After 56 days, new bone marrow aspirate samples for cytogenetic assessment should be re-collected at the time of the bone marrow assessment. An individual patient may be re-screened up to three times for the study. Once the number of patients screened and enrolled is likely to ensure target enrollment, the Sponsor may close the study to further screening. In this case, the patients who screen failed will not be permitted to re-screen.

8.1.1 Eligibility screening

Following registering in the IRT for screening, participant eligibility will be checked once all screening procedures are completed. The eligibility check will be embedded in the IRT system. Please refer and comply with detailed guidelines in the IRT manual.

8.1.2 Information to be collected on screening failures

Patients who sign an informed consent but fail to be enrolled for any reason will be considered a screen failure. The reason for not being enrolled will be entered on the Disposition Page. The demographic information, informed consent, and Inclusion/Exclusion pages must also be completed for Screen Failure patients. No other data will be entered into the clinical database for patients who are screen failures, unless the patient experienced a Serious Adverse Event during the Screening Phase (see [Section 10.1.4](#) for SAE reporting details). If the patient fails to be enrolled, the IRT must be notified within 2 days of the screen fail that the patient was not enrolled. The reason for screen failure should be recorded on the appropriate Case Report Form.

8.2 Participant demographics/other baseline characteristics

Country-specific regulations should be considered for the collection of demographic and baseline characteristics in alignment with CRF.

Patient demographics and baseline characteristics collected will include the following: age at consent, gender (and childbearing potential for female), race/ethnicity, height, weight, all relevant medical history including cardiovascular disease history, CML disease history, including mutation status, and prior and concomitant medication including prior TKI therapy and antineoplastic medication.

Participant race/ethnicity data are collected and analyzed to identify any differences in the safety and/or efficacy profile of the treatment due to these characteristics. In addition, we need to assess the diversity of the study population as required by Health Authorities.

Physical examination including extramedullary involvement, ECOG performance status, vital signs, ECGs, Echocardiography, and laboratory assessments will be performed at screening.

Significant findings that were present prior to the signing of informed consent must be included in the Relevant Medical History/Current Medical Conditions page on the subject's eCRF. Significant new findings that begin or worsen after informed consent must be recorded on the AE page of the patient's eCRF.

The local reading of the screening ECG, echocardiograms as well as the central results of the qualitative PCR, RQ-PCR and the local cytogenetic assessment (BMA) within 56 days before Week 1 Day 1 must be available prior to enrollment and first dose of study treatment to evaluate eligibility. Central mutation analysis will be performed during the course of the study and not available prior to enrollment.

8.3 Efficacy

8.3.1 Efficacy assessments

If the COVID-19 pandemic limits or prevents on-site study visits, alternative methods of providing continuing care may be implemented. Phone calls, virtual contacts (e.g. teleconsult) or visits by site staff/home nursing service to the participant's home depending on local regulations and capabilities, can replace on-site study visits, for the duration of the pandemic or until it is safe for the participant to visit the site again. If participants cannot visit the site for protocol specified assessments and that visit by site staff/home nursing service to the participant's home may not be done, an alternative laboratory (local) collection may be used.

8.3.1.1 Molecular response

Molecular response (MR) will be assessed in all patients.

Levels of BCR-ABL1 transcripts will be determined by real-time quantitative PCR (RQ-PCR) testing of peripheral blood and analyzed centrally. Log reduction in BCR- ABL1 transcripts levels from the standardized baseline value, or the percent ratio of BCR-ABL1 transcripts versus control gene (ABL1) transcripts converted to a reference standard, international scale (IS) ([Hughes and Branford 2006](#)), will be calculated for each sample.

Major molecular response and related variables are defined as the following:

- Rate of MMR where MMR is defined as a ≥ 3.0 log reduction in BCR-ABL1 transcripts compared to the standardized baseline equivalent to ≤ 0.1 % BCR-ABL1/ABL1 % by IS as measured by RQ-PCR, confirmed by duplicate analysis of the same sample,
- Time to MMR defined as the time from the date of enrollment to the date of the first documented MMR,
- Duration of MMR defined as the time from the date of first documented MMR to the earliest date of loss of MMR, progression to AP or BC, or CML-related death.
- Rate of Deep Molecular Responses MR4 and MR4.5 are defined as a ≥ 4 log or ≥ 4.5 log reduction in BCR-ABL1 transcripts compared to the standard baseline equivalent to 0.01 % or 0.0032% BCR-ABL1/ABL by IS as measured by RQ-PCR, confirmed by duplicate analysis of the same sample with at least 10,000 or 32,000 ABL1 transcripts, respectively.

Loss of MMR is defined as increase of BCR-ABL1/ABL to $> 0.1\%$ by international scale (IS) in association with a ≥ 5 -fold rise in BCR-ABL1 from the lowest value achieved on study

treatment and replicated by a second analysis of the same sample. Loss of MMR confirmed by subsequent sample analysis within 4 to 6 weeks showing loss of MMR associated with a ≥ 5 -fold rise in BCR-ABL1 from the lowest value achieved on study treatment, unless it is associated with confirmed loss of CHR or loss of CCyR or progression to AP/BC or CML-related death. The blood samples will be taken as described in [Table 8-1](#) and [Table 8-2](#).

If at one visit the sample is missing during transit to the central PCR laboratory, or the PCR result is difficult to interpret or sample not analyzable, or if the PCR sample was not collected, a subsequent unscheduled visit sample must be collected within 4 weeks either at the next scheduled visit (week 4 or week 8) or as an unscheduled visit.

Table 8-2 Blood samples (efficacy primary endpoint)

Sample Type	Volume	Visit
Blood for BCR-ABL1 quantification by RQ-PCR	20 mL	Screening/Baseline
	20 mL	Week 12
	20 mL	Week 24
	20 mL	Week 36
	20 mL	Week 48
	20 mL	Every 12 weeks thereafter up to week 132 (w60, w72, w84, w96, w108, w120, w132)
	20 mL	End of Treatment

8.3.1.2 Bone marrow analysis and cytogenetics

Cytogenetic response will be assessed as the percentage of Ph+ metaphases in the bone marrow and is defined as the following (a review of a minimum of 20 metaphases is required):

- Major (MCyR) - 0 to 35% Ph+ metaphases
- Complete (CCyR) - 0% Ph+ metaphases
- Partial (PCyR) - >0 to 35% Ph+ metaphases
- Minor (mCyR) - >35 to 65% Ph+ metaphases
- Minimal - >65 to 95% Ph+ metaphases
- None - >95 to 100% Ph+ metaphases.

Bone marrow aspirate for cytogenetic analyses will be performed at screening/baseline (performed up to 56 days prior to Week 1 Day 1), at Week 48 and at EOT (only required if the patient discontinues from the study early due to lack/loss of response). Should bone marrow assessments have been performed before the main informed consent is signed but within 56 days of Week 1 Day 1, no further bone marrow sampling will be required at screening and local assessment data will be collected.

Quantification of the percentage of Ph+ chromosome metaphases, number of metaphases, number positive for Ph chromosome, additional chromosomal abnormalities as well as data from cytologic evaluation (microscopic analysis) of percentage of blasts and promyelocytes

will be recorded on the Bone Marrow eCRF. These exams will be performed and analyzed locally.

8.3.1.3 Hematologic response

A complete hematologic response (CHR) is defined as all of the following present for ≥ 4 weeks:

- WBC count $<10 \times 10^9/L$
- Platelet count $<450 \times 10^9/L$
- Basophils $<5\%$
- No blasts and promyelocytes in peripheral blood
- Myelocytes + metamyelocytes $< 5\%$ in peripheral blood
- No evidence of extramedullary disease, including spleen and liver

8.3.2 Appropriateness of efficacy assessments

Assessing molecular response with RQ-PCR is considered as standard in CML therapy and recommended in treatment guidelines (Hochhaus et al 2020a). In order to review individual responses against the milestones in treatment recommendations and to allow for the comparison of trial results against other data, the molecular responses will be reported as standardized results to International Scale (IS) (Cross et al 2015).

8.4 Safety and tolerability assessments

Safety will be monitored by the assessments described below, in addition to the collection of adverse events at every visit. For details on AE collection and reporting, refer to Section 10. Significant findings that were present prior to the signing of informed consent must be included in the Relevant Medical History/Current Medical Conditions page on the patient's eCRF. Significant new findings that begin or worsen after informed consent must be recorded on the AE page of the patient's eCRF.

As per Section 4.6, if the COVID-19 pandemic limits or prevents on-site study visits, regular phone or virtual calls can occur as outlined in the Visit Schedule (or more frequently if needed) for safety monitoring and discussion of the participant's health status until it is safe for the participant to visit the site again. If participants cannot visit the site for protocol specified safety lab assessments or that central laboratory analysis cannot be performed due to COVID-19 pandemic consequences, an alternative laboratory (local) collection site may be used. Assessments of blood pressure, heart rate, weight, ECG and blood collection may also be conducted off-site by healthcare professional visits to the participant's off-site location (please refer to Section 4.6).

Table 8-3 Physical examination, vital sign and height and weight assessments

Assessment	Specification
Physical examination	A complete physical examination will include the examination of general appearance, skin, neck (including thyroid), eyes, ears, nose, throat, lungs, heart, abdomen, back, lymph nodes, extremities, vascular and neurological. Information about the physical examination must be present in the source

	documentation at the study center and will be collected at the visits specified in Table 8-1 . Presence of extramedullary leukemic involvement will be checked at the physical examination at screening/baseline. Findings on physical examination consistent with extra- medullary leukemic involvement will be recorded (e.g. liver and spleen size, any other organ involvement).
Vital signs	Vital signs include blood pressure (supine position when ECG is collected), pulse measurement, and body temperature and are performed at the visits as specified in Table 8-1 .
Height and weight	Height in centimeters (cm) and body weight (to the nearest 0.1 kilogram (kg)) will be measured as specified in Table 8-1 .

8.4.1 Performance status

ECOG Performance status scale will be used as described in [Table 8-4](#) at the visits specified in [Table 8-1](#).

Table 8-4 ECOG Performance status scale

Description	Grade
Fully active, able to carry on all pre-disease activities without restriction.	0
Restricted in physically strenuous activity but ambulatory and able to carry out work of a light or sedentary nature e.g. light housework, office work.	1
Ambulatory and capable of all self-care but unable to carry out any work activities. Up and about more than 50% of waking hours.	2
Capable of only limited self-care, confined to bed or chair more than 50% of waking hours.	3
Completely disabled. Cannot carry on any self-care. Totally confined to bed or chair.	4
Dead.	5

8.4.2 Laboratory evaluations

Central laboratory will be used for analysis of hematology, biochemistry, coagulation, serum pregnancy and hepatitis marker specimens collected (safety monitoring) as specified in [Table 8-1](#). The time windows granted for laboratory evaluations are identical with the corresponding visit time windows for each visit (see [Section 8](#)).

Additional unscheduled blood draws may be performed at the discretion of the investigator at any time during the study. For example, if the PCR sample was lost during transit or result is difficult to analyze, to confirm a loss of response to study treatment or as clinically indicated.

If the COVID-19 pandemic limits or prevents on-site study visits, if pre-agreed with Novartis and considered by the Investigator it is in the interest of the participant's health to perform study procedures remotely, safety samples that can be collected remotely will be collected and analyzed in line with the study laboratory manual. If participants cannot visit the site for protocol specified safety lab assessments or in case of central lab logistical challenges an alternative laboratory (local) collection site may be used. Please note that BCR-ABL1 quantification must be performed centrally. Where samples are collected and analyzed at a local laboratory instead of the central laboratory, Novartis will ensure the results reported for

hematology and chemistry described below are equivalent to central laboratory collection and analysis by collecting the local normal ranges.

Table 8-5 Central clinical laboratory parameters collection plan

Test category	Test Name
Hematology	Hemoglobin, platelets, red blood cells, white blood cells, WBC morphology with differential (basophils, eosinophils, lymphocytes, monocytes, neutrophils, promyelocytes, myelocytes, metamyelocytes, blast and other)
Chemistry	Albumin, alkaline phosphatase, ALT (SGPT), AST (SGOT), total calcium, total calcium (corrected for albumin), creatinine, creatine kinase, potassium, magnesium, sodium, phosphate (inorganic phosphorus), direct bilirubin, indirect bilirubin, total bilirubin, total cholesterol, LDL cholesterol, HDL cholesterol, total protein, triglycerides, blood urea or Blood Urea Nitrogen (BUN), uric acid, amylase, lipase, serum glucose (fasting), Hemoglobin A1c (at screening only), Creatinine clearance (Cockcroft-Gault formula)
Coagulation	International Normalized Ratio (INR), Activated Partial Thromboplastin Time (aPTT)
Hepatitis markers	HbsAg, HbcAb /anti-Hbc, HBV-DNA (if anti-Hbc and HbsAg are positive), HCV Ab, HCV-RNA (if HCV Ab is positive).
Liver assessments (for DILI) (see Section 6.6.4.1)	ALT, AST, albumin, creatinine kinase, total bilirubin, direct and indirect bilirubin, GGT, prothrombin time (PT)/INR and alkaline phosphatase
Pregnancy Test	Serum beta fraction of human chorionic gonadotropin (β -HCG) testing (at screening and EOT). Urine pregnancy test will be done monthly for women of childbearing potential (will be done locally).

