9. Testing for Hepatitis B surface antigen (HbsAg) and Hepatitis B core antibody (HBcAb / anti HBc) will be performed at screening. Patients with active Hepatitis B Virus (HBV) infection (hepatitis B surface antigen [HbsAg] positive) will be excluded. HBV-DNA testing will also be performed at screening, if anti Hbc is positive. Note: Patients with antecedent but no active HBV (i.e., hepatitis B core antibody [HBcAb] positive, and both HbsAg and HBV-deoxyribonucleic acid negative) are eligible. In these cases, patients may be on anti-HBV prophylaxis and should be monitored for reactivation via monthly HBV-DNA evaluations.
10. Positive test for Hepatitis C Virus (HCV) ribonucleic acid (RNA). Testing for Hepatitis C antibody (HCV Ab) will be performed at screening. HCV-RNA testing will also be performed at screening if HCV Ab are positive.

11. Impairment of gastrointestinal (GI) function or GI disease that may significantly alter the absorption of study drug (e.g. ulcerative disease, uncontrolled nausea, vomiting, diarrhea, malabsorption syndrome, small bowel resection, or gastric bypass surgery)
12. Previous treatment with or known/ suspected hypersensitivity to asciminib or any of its excipients.
13. Pregnant or nursing (lactating) women
14. Women of child-bearing potential, defined as all women physiologically capable of becoming pregnant, unless they are using highly effective methods of contraception during dosing and for 3 days after last dose of asciminib. If local regulations or locally approved prescribing information are more stringent than the protocol required duration of contraception, the longer duration must be followed.

Highly effective contraception methods include:

- Total abstinence (when this is in line with the preferred and usual lifestyle of the subject. Periodic abstinence (e.g., calendar, ovulation, symptothermal, post-ovulation methods) and withdrawal are not acceptable methods of contraception.
- Female sterilization (have had surgical bilateral oophorectomy (with or without hysterectomy) total hysterectomy or bilateral tubal ligation at least six weeks before taking study treatment). In case of oophorectomy alone, only when the reproductive status of the woman has been confirmed by follow up hormone level assessment.

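### Table 8-5 sets an HBV-DNA trigger that misses the only patients whose eligibility depends on the result

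*Protocol*

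**What the plan says.** Protocol Section 5.2, exclusion criterion 9, does three things.

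- It bars active infection, identified by surface antigen: "Patients with active Hepatitis B Virus (HBV) infection (hepatitis B surface antigen [HbsAg] positive) will be excluded".
- It sets the condition for the viral load test: "HBV-DNA testing will also be performed at screening, if anti Hbc is positive".
- It admits patients with past but inactive infection, described as "hepatitis B core antibody [HBcAb] positive, and both HbsAg and HBV-deoxyribonucleic acid negative", and asks for monthly HBV-DNA follow-up in them.

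Table 8-5 in Section 8.4.2 lists the hepatitis markers for the central laboratory. Its entry for viral load is "HBV-DNA (if anti-Hbc and HbsAg are positive").

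Both statements concern the same step. Section 8.1 counts hepatitis markers among the screening tests: "laboratory baseline assessments (including hematology, chemistry, coagulation, serum pregnancy test and hepatitis markers"). Section 8.4.2 sends those specimens to the central laboratory: "Central laboratory will be used for analysis of hematology, biochemistry, coagulation, serum pregnancy and hepatitis marker specimens collected".

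**The concern.** The two conditions are not the same. Criterion 9 asks for HBV-DNA whenever anti-HBc is positive, whatever the HBsAg result. Table 8-5 asks for it only when both markers are positive. A patient with both markers positive is excluded on HBsAg, so the HBV-DNA result cannot change that patient's status. A patient who is anti-HBc positive and HBsAg negative cannot be shown to be eligible without it, and the table as worded does not order it.

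What is at stake is safety screening. Section 10.2 recognises that HBV can reactivate in HBsAg-negative, anti-HBc-positive people and says the risk should be monitored, so the protocol itself regards the omitted group as one to watch. If the table's condition were carried into the central laboratory set-up, no HBV-DNA result would be produced for these patients by default, and someone would have to notice the gap before enrolment.

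**Working it through.** No numerical figure in the plan is involved, so the check is a comparison of the two rules over every combination of the two markers.

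**Inputs**

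- Criterion 9 trigger (Section 5.2): anti-HBc positive.
- Table 8-5 trigger (Section 8.4.2), read literally: anti-HBc positive and HBsAg positive.
- Table 8-5 trigger, read loosely: either marker positive.
- Eligibility (Section 5.2): HBsAg positive means excluded. Anti-HBc positive with HBsAg negative means eligible only if HBV-DNA is negative.

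**Comparison**

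| anti-HBc | HBsAg | Criterion 9 tests? | Table 8-5, literal | Table 8-5, read as either | HBV status for eligibility |
|---|---|---|---|---|---|
| + | + | yes | yes | yes | excluded on HBsAg |
| + | − | yes | **no** | yes | depends on HBV-DNA |
| − | + | no | no | **yes** | excluded on HBsAg |
| − | − | no | no | no | not excluded on HBV |

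**Result**

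- Literal reading: agreement in 3 of 4 patterns. The mismatch is anti-HBc positive, HBsAg negative, the only row in which HBV-DNA decides eligibility.
- Of the 2 patterns not excluded on HBsAg, criterion 9 triggers the test in 1 and the literal table in 0.
- Loose reading: again 3 of 4. The mismatch moves to anti-HBc negative, HBsAg positive. Those patients are excluded anyway, so eligibility would not be affected.
- Neither reading makes the table identical to criterion 9.

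These are counts of logical patterns, not of patients.

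**Comparison with hepatitis C**

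The neighbouring entry in the same table cell is "HCV-RNA (if HCV Ab is positive"), and criterion 10 says "HCV-RNA testing will also be performed at screening if HCV Ab are positive". These agree in both possible patterns (antibody positive, antibody negative: 2 of 2). The table therefore restates its criterion correctly for HCV and departs from it only for HBV, which points to an isolated slip.

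**Intent**

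The Amendment 01 summary, used here only as evidence of intent, describes the Section 5.2 clarification as making HBV-DNA depend on a positive anti-HBc, with no need for it when HBsAg is positive. That supports criterion 9 over the table. The finding does not rest on it, because both conflicting statements stand in current text.

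**The case against.** The best case against giving this weight is that the operative rule is already correct elsewhere. Criterion 9 states the trigger, the eligibility condition and the follow-up. Section 5 makes the investigator responsible for ensuring that no exclusion criterion is met, Section 8.1.1 adds an eligibility check in the IRT, Section 11.3 requires monitors to verify adherence to the criteria, and Section 8.4.2 allows unscheduled blood draws. A site that followed the table alone would find itself without a result that criterion 9 requires. The likely consequence is a delay or an extra sample, and wrongful enrolment would need criterion 9 to be overlooked as well. The laboratory manual and the hepatitis row of Table 8-1 were not available, so the central laboratory may already have been testing on anti-HBc alone. The table's wording may also have been loose shorthand for either marker, in which case eligibility is untouched.

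Most of this stands, and it limits the size of the point. It does not remove the discrepancy. The controls work by catching a gap that the table creates, and the IRT and monitoring sections describe general checks without naming HBV-DNA. The loose reading is the less natural one and still does not match criterion 9. It is also fair to say that nobody is likely to have chosen to test only excluded patients: this is a wording inconsistency, not a considered design decision.

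**Conclusion.** The inconsistency is real and rests on the protocol's current wording alone. Read literally, Table 8-5 directs HBV-DNA testing to patients whose eligibility is already settled and leaves out the one group for whom it matters. The two triggers differ in one of four marker patterns.

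The practical size is small. It does not touch the estimand, sample size, power or primary analysis. The documents do not show that any test was omitted, and they do not give the number of anti-HBc-positive patients, which could be zero. The conclusion assumes that the word joining the two markers in the table means both. If it means either, the mismatch falls only on excluded patients and the point becomes editorial. No claim is made about the monthly HBV-DNA follow-up, which criterion 9 states and whose scheduling cannot be checked in the text available.

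The sponsor should correct it: the table is the protocol's list of central laboratory tests, its stated condition is wrong for an eligibility-determining safety test, and the correction is almost free.

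**What to change.** Change the Table 8-5 entry to read *HBV-DNA (if anti-HBc is positive)*, which reproduces criterion 9 in all four patterns. Adding a further condition that HBsAg be negative would save a test in patients already excluded, but the table would then differ from criterion 9 in the both-positive pattern unless the criterion were changed too. The simpler wording is preferable.

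Confirm that the laboratory manual and the central laboratory's ordering rule use the same trigger. A cross-reference from the table to criterion 9 for the monthly follow-up is optional.

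The cost is one table cell at the next amendment and one check of the laboratory manual.
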